	CTCAE grade 3 edema lasting fewer than 5 days
	Grade 3 laboratory abnormalities that are responsive to oral supplementation or deemed by the investigator to be not clinically significant
CTCAE version 4.03 will be used for all grading. Optimal therapy for vomiting or diarrhea will be based in institutional guidelines, with consideration of the prohibited medications listed in this protocol.	

7.5 Phase II - The phase II study in pancreatic cancer will depend on the successful completion of the phase I trial, determination of the recommended dose level and discussion between PI and co-sponsors of the study.

7.51 Following the accrual of the first 6 patients into the phase II portion, we will assess for any unexpected serious toxicities (without halting accrual). If >1 of the first 6 patients experience grade 5 toxicity at least possibly (possible, probable, definite) related to treatment, we will halt accrual and discuss with the sponsors alternative dose levels including the possibility to de-escalate to one dose level. After reinitiating accrual, the patients who were included in the prior dose level cannot be considered for the final analysis and will have to be replaced.

7.52 In the Phase II portion of this study, all patients' tissue samples will be screened for HRD and BRCA-like signature, and only those patients with defects will be selected for the treatment study.

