16.5 Data & Safety Monitoring

16.51 This study will be monitored by the Mayo Data Safety Monitoring Board (DSMB) every 6 months. Toxicity, efficacy and administrative information for this trial will be reviewed by the study team routinely.

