16.52 Adverse Event Stopping Rules

The stopping rules specified below are based on the knowledge available at study development. We note that the Adverse Event Stopping Rule may be adjusted in the event of either (1) the study reopening to accrual or (2) at any time during the conduct of the trial and in consideration of newly acquired information regarding the adverse event profile of the treatment(s) under investigation. The study team may choose to suspend accrual because of unexpected adverse event profiles that have not crossed the specified rule below.

16.521 Phase I/Ib Adverse Event Stopping Rule

During the first 2 cycles, 4 of the initial 10 treated patients or 40% or more of all patients (i.e., when accrual is greater than 10 patients) have experienced a Grade 4+ adverse event at least possibly related to study treatment, per NCI Common Terminology Criteria for Adverse Events v.5.0, excluding the following:

- Grade 4 neutrophil count decreased lasting ≤ 7 days
- Grade 4 white blood cell decreased lasting ≤ 7 days
- Grade 4 platelet count decreased lasting ≤ 7 days
- Grade 4 diarrhea responding to optimal support

16.522 Phase II Adverse Event Stopping Rules

Accrual will be temporarily suspended to this study if at any time we observe events considered at least possibly related to study treatment (i.e. an adverse event with attribute specified as “possible”, “probable”, or “definite”) that satisfy either of the following:

- If 1 or more patients out of the first 6 patients (either HRD encompassing BRCA1, BRCA2, PALB2 or other HRD) experience grade 5 events (death) deemed at least possible (possible, probably, or definite) related to MFR, the accrual to the study will be suspended to allow for investigation. After consideration by the study team (study chair, statistician) and consultation with the sponsor, a decision will be made as to whether accrual can be resumed.
- If 6 or more patients among the first 20 patients (either HRD encompassing BRCA1, BRCA2, PALB2 or other HRD) enrolled

or 30% of the patients thereafter develop a grade4+ non-hematologic toxicities at least possible (possibly, probably or definitely) related to treatment, enrollment will be suspended so that the adverse event data can be examined and a trial recommendation will be formulated and presented to Mayo DSMB.

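### Section 16.522 specifies no DSMB step before Phase II accrual resumes after a related death in the first 6 patients, although its toxicity-rate trigger does go to the DSMB

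*Combined protocol and SAP*

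**What the plan says.** Section 16.522 gives two Phase II triggers for suspending accrual, each with its own follow-up.

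- **Grade 5 trigger (first bullet).** It opens "If 1 or more patients out of the first 6 patients" and covers deaths judged at least possibly related to the regimen. When it is met, "the accrual to the study will be suspended to allow for investigation". The bullet then gives the path to reopening: "After consideration by the study team (study chair, statistician) and consultation with the sponsor, a decision will be made". The DSMB is not mentioned.
- **Toxicity-rate trigger (second bullet).** It opens "If 6 or more patients among the first 20 patients", with a 30% rule after that, and counts related non-hematologic toxicity of grade 4 or higher. Enrollment is suspended, the data are examined, and "a trial recommendation will be formulated and presented to Mayo DSMB".

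Two other places bear on the point. Section 16.51 sets the general schedule: "This study will be monitored by the Mayo Data Safety Monitoring Board (DSMB) every 6 months". Section 7.51 has its own grade 5 rule for the first 6 Phase II patients, triggered by more than 1 death. There the action is "we will halt accrual and discuss with the sponsors alternative dose levels". The DSMB is not mentioned there either.

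**The concern.** The trial has a DSMB and uses it when a toxicity rate is crossed. For a related death early in Phase II, the written path runs only through the study team and the sponsor. Following it exactly, accrual can reopen with no required independent review of the death, and the board may first see it at its next scheduled meeting.

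This is an open-label, single-arm study, and 10.4 refers to a sponsor-investigator. Consulting the sponsor may therefore add little independence. At stake is whether further patients are exposed to a combination with a suspected fatal toxicity before anyone outside the trial's conduct has reviewed the case. The point is about who reviews the restart. It is not about the trigger threshold or the dose.

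**Working it through.** The plan states no operating figure for these safety rules, so there is nothing to reproduce. The check is a comparison of the text, followed by two calculations for scale.

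**1. The routes side by side**

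| Rule | Trigger | Stated review after suspension | DSMB step |
|---|---|---|---|
| 16.522, first bullet | 1 or more related deaths in first 6 | Study team considers, sponsor consulted | None specified |
| 7.51 | More than 1 related death in first 6 | Discussion with sponsors of dose levels | None specified |
| 16.522, second bullet | 6 or more of first 20, then 30%, related grade 4+ non-hematologic | Data examined, recommendation formulated | Presented to DSMB |
| 16.51 | None (calendar) | Every 6 months | Yes, not tied to an event |

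The second bullet does not cover the gap. It counts grade 5 non-hematologic events, but one death in 6 patients is far short of 6 events.

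The reporting rules do not cover it either. Section 10.312 requires 24-hour reporting of deaths. Under 10.4, reports go to the coordinating group's safety office, on to the two drug suppliers and, where required, to the FDA. Section 10.51 sends qualifying events to the local IRB. None of these routes includes the DSMB.

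**2. Could the grade 5 trigger plausibly be met?** The documents give no related-death rate, so p is an assumption, shown over a range. For 16.522, P(at least 1 of 6) = 1 − (1 − p)^6. For 7.51, P(at least 2 of 6) = 1 − (1 − p)^6 − 6p(1 − p)^5.

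| Assumed p | 16.522 (1 or more) | 7.51 (more than 1) |
|---|---|---|
| 1% | 5.9% | 0.15% |
| 2% | 11.4% | 0.6% |
| 5% | 26.5% | 3.3% |
| 10% | 46.9% | 11.4% |

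**3. How many patients could enrol before the next scheduled review?** Inputs: maximum of 52 Phase II patients, being 24 with BRCA1, BRCA2 or PALB2 mutations and 28 with other HRD (16.12); 1 to 2 mutation carriers per month and an accrual period of 12 to 24 months (16.13); review every 6 months (16.51). The plan gives no rate for the other-HRD group. The assumption is that its 28 patients accrue evenly over the same 12 to 24 months.

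- Other-HRD rate: 28/24 = 1.2 to 28/12 = 2.3 per month.
- Total rate: 52/24 = 2.2 to 52/12 = 4.3 per month.
- Full 6-month interval: 52 × 6/24 = 13 to 52 × 6/12 = 26 patients, or 25% to 50% of 52.
- Restart equally likely at any point in the interval: half of that on average, about 6.5 to 13 patients.

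**The case against.** The strongest reply is that the plan omits a DSMB step but does not exclude the DSMB. The study team could consult it at any time, and the board's regular review continues. Deaths are reported within 24 hours, the suppliers and possibly the FDA are told, and 16.52 lets the study team suspend accrual below the stated thresholds. After a restart, the toxicity-rate rule still applies and leads to the DSMB. All of this is true. None of it requires the board to see the death before accrual reopens, and the purpose of a prespecified rule is to fix that route in advance.

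Several stronger readings are tempting, and the documents do not support them.

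- A reader might infer that the trigger sent to the DSMB is a non-fatal one. It covers grade 4 and above, so it includes deaths. The accurate statement is that non-fatal events alone can meet it. The two triggers also differ in kind, an early death count against a toxicity rate, so ranking them by seriousness is a judgement.
- A reader might infer that the second bullet bars resumption until the DSMB agrees. It requires only that a recommendation be presented.
- A reader might infer that the study chair, statistician and sponsor are named as the deciders. The text gives consideration by the team and consultation with the sponsor, and leaves the decider unstated.
- Section 7.51 is limited corroboration. Its trigger is higher, and its text concerns discussion of dose levels, not who authorises the restart.

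**Conclusion.** The concern holds as a gap in the stated review route. After a related death in the first 6 Phase II patients, no section requires DSMB review before accrual resumes, while 16.522 does bring the DSMB in for its other trigger. The documents give no reason for the difference.

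The exposure is at most about 13 to 26 patients. It should not be read as an expected number. It assumes the full 52 patients, even accrual of both groups over 12 to 24 months, and a restart just after a scheduled DSMB review; the average over restart times is about half. The chance that the rule is invoked depends on an unknown death rate. Under the 16.522 trigger it runs from 5.9% to 46.9% for assumed rates of 1% to 10%, so the situation cannot be dismissed as remote.

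This does not affect the validity of the primary analysis. It is a safety-governance point that should be corrected because the remedy is cheap.

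**What to change.** Add to the first bullet of 16.522 that the adverse event data and the study team's recommendation are presented to the Mayo DSMB before accrual resumes. This goes further than the second bullet, which has no timing requirement; the same wording could be used there for consistency.

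Apply the same review route in 7.51. In the same amendment, reconcile the two grade 5 triggers (more than 1 of 6 in 7.51, 1 or more of 6 in 16.522). Which of them is intended is for the study team to state.

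The cost is a short edit in two sections. If the trigger is met, it adds one ad hoc DSMB review and a short delay while accrual is already suspended.

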17.0 Pathology Considerations/Tissue Biospecimens

17.1 Tissue Biospecimen Submission

17.11 Summary Table of Tissue Biospecimens for This Protocol

Type of tissue biospecimen to submit	Mandatory or optional	When to submit	Reason for submission (background/methodology section)	Where to find specific details for biospecimen submission
Formalin-fixed paraffin-embedded (FFPE) tissue blocks with corresponding H&E (OR total of 10 unstained (5) micron slides with corresponding H&E)	Mandatory	≤60 days after registration	Correlative studies (Section 17.3)	Section 17.2

If an institution is not able to provide the tissue, it does not cause the patient to be ineligible; however the collection of these tissues is **strongly recommended.*

17.2 Paraffin Embedded Tissue Blocks/Slides (mandatory for research tissue)

17.21 Submit one formalin fixed paraffin-embedded (FFPE) tumor tissue block from the original and/or recurrent surgery with largest amount of invasive tumor (at least 1 cm of tumor for cases of surgical resection).

17.22 The FFPE tissue block is preferred; however, if an institution is unable to provide a tissue block, cut 10 five-micron unstained slides with corresponding H&E and mount on charged glass slides. Label the slides with the ACCRU patient ID number, accession number, and order of sections (i.e., 1-10). H&E stain the first cut slide (i.e., slide labeled 1). For samples containing less than 7 square millimeters of tumor tissue, multiple sections should be mounted onto each slide to ensure that the appropriate amount of tumor tissue is available. Ideally, each slide must have a minimum of 75% tumor tissue on the slide to be deemed adequate for study. Do not bake or place cover slips on the slides. Please do NOT use sticky labels on slides.

17.23 The following materials below are mandatory (unless indicated otherwise) and required for shipment:

- Paraffin embedded tissue blocks with corresponding H&E slide (OR 10 unstained slides with corresponding H&E(s), per instructions in Section 17.22).
- Specimen Submission: Tissue Baseline form
- Surgical Pathology Report
- Operative Report (*optional*)

Note: Please make sure each slide is labeled with the specimen surgical pathology number, block number and order of sections cut either via your institution's standard method for labeling or using a permanent marker.

Labeling with sticky labels is not acceptable.

17.24 The block/slides must be appropriately packed to prevent damage (e.g., slides should be placed in appropriate slide container) and placed in an individual plastic bag. Label the bag with the protocol number, ACCRU patient ID number, and patient initials. During warm weather months, paraffin blocks should be shipped using a refrigerant pack to avoid heat that may melt paraffin and damage blocks.

17.25 Tissue specimens must be shipped **≤60** days after registration.

17.26 Verify that the appropriate sections of the Specimen Submission: Tissue Baseline form are completed and filled in correctly. Enter information from the Specimen Submission: Tissue Baseline form into the remote data entry system on the same day the specimen is submitted (see CRF Packet).

17.27 Ship all block/slide tissue specimens and accompanying materials to the ACCRU Research Base:

17.28 When an appropriate request is submitted, the ACCRU Operations Office will forward the block/slides to the ACCRU Research Base Pathology Research Core, Mayo Clinic Rochester for processing.

17.29 Frozen Tumor tissue: (None)

17.3 Study Methodology and Storage Information

17.31 Submitted tissue samples will be analyzed as follows:

Tissue from biopsies will be processed at a Clovis 3rd party diagnostic collaborator to obtain comprehensive genomic profiling (CGP) using hybridization capture of all coding exons of >300 cancer-related genes and 31 genes commonly rearranged in cancer. To this end ≥50ng of DNA will be extracted from FFPE specimens. All tumors will be sequenced to high (average

>570X), uniform coverage. Genomic alterations (base substitutions, small indels, rearrangements and copy number alterations) will be determined in tissue from tumor biopsies.

We will test whether HRD in tumor samples is associated with clinical outcome including the following (among others): response to therapy, progression-free survival, and overall survival.

- 17.32 At the completion of the study, any unused/remaining material will be stored in the ACCRU Central Operations Office (Attn.: Pathology Coordinator) for future research according to the patient consent permission (see Section 6.15). Potential future research may include immunohistochemistry (IHC) analyses to analyze predictive biomarkers, changes in expression pattern with therapy, and correlation with response and/or adverse events. When a protocol is developed, it will be presented for IRB review and approval.
- 17.33 Banking of tumor tissue, according to the patient consent permission (see Section 6.32), is for future research. As protocols are developed, they will be presented for ACCRU and IRB review and approval. (This collection is part of a general strategy of investigation for ACCRU studies).
- 17.34 The institutional pathologist will be notified by the Pathology Coordinator if the block may be depleted.
- 17.35 Blocks requested to accommodate individual patient management will be returned promptly upon request.

17.4 Return of Genetic Testing Research Results

Because the results generated by the genetic testing included in this section are not currently anticipated to have clinical relevance to the patient or their family members, the genetic results will not be disclosed to the patients or their physicians.

If, at any time, genetic results are obtained that may have clinical relevance, IRB review and approval will be sought regarding the most appropriate manner of disclosure and whether or not validation in a CLIA certified setting will be required. Sharing of research data with individual patients should only occur when data have been validated by multiple studies and testing has been done in CLIA-approved laboratories.

18.0 Records and Data Collection Procedures

The RAVE system will be used to collect data. Access the RAVE system through the iMedidata portal at [REDACTED] All data must be entered by Remote Date Entry (RDE) and completed by qualified and authorized personnel. All data on the CRF must reflect the corresponding source document. Please refer to the ACCRU website for instructions

[REDACTED]

18.1 Submission Timetables

Pre-Registration Material(s) – Phase II Only

Case Report Form (CRF)	Active-Monitoring Phase (Compliance with Test Schedule Section 4.0)
Screening (Phase II only)	Complete only if patient is NOT registered after he/she is pre-registered

Initial Material(s)

CRF	Active-Monitoring Phase (Compliance with Test Schedule Section 4.0)
Institutional Contacts	
Phase of Study	
On-Study	
On-Study: Pancreatic Cancer ²	
On-Study: Gastroesophageal Cancer ²	
On-Study: Colorectal Cancer ²	
On-Study: Biliary Tract Cancer ²	
On-Study: Prior Surgery ²	
On-Study: Prior Radiation ²	
On-Study: Prior Neoadjuvant, Adjuvant or Metastatic Therapies ²	
Laboratory Tests & Results: Baseline	
Adverse Events: Baseline	
RECIST Measurements: Baseline	
Supporting Documentation: Baseline ¹	
Specimen Submission: Blood Baseline (see Section 14.0)	
Specimen Submission: Tissue Baseline (see Section 17.0)	
Patient Status: Baseline	
OP and Path Reports (see Section 17.0) ¹	
Off Treatment ²	Submit ≤2 weeks after registration if withdrawal/refusal occurs prior to beginning protocol therapy
ACCRU Deviation Form ²	Submit only if applicable during all phases of the study (initial, active and observation)

1. Upload Op, Path Reports, and tumor molecular profiling report (if available) via the Supporting Documentation: Baseline form. This is in addition to the pathology material requirements for tissue submission (Section 17.0).
2. Submit only if applicable.

Test Schedule Material(s)

CRF	Active-Monitoring Phase (Compliance with Test Schedule Section 4.0)		
	At each evaluation during treatment	At end of treatment	Observation
Treatment (Intervention)	X	X	
Treatment (Intervention): Dose Modifications, Omissions and Delays ²	X		
Adverse Events: Solicited	X	X	
Adverse Events: Other ²	X	X	
Dose Limiting Toxicities (Phase I only) ²	X		
RECIST Measurements ¹	X	X	X
Supporting Documentation ¹	X	X	X
Day 1 Laboratory Tests and Results ³	X		
Day 15 Laboratory Tests and Results ⁴	X		
Specimen Submission: Blood	X (see Section 14.0)		
Patient Status: Treatment (Intervention)	X	X	
Notice of New Primary ²	X	X	X
Consent Withdrawal (choose appropriate form) ³			
• Consent Withdrawal: Specimen Only	X	X	X
• Consent Withdrawal: Clinical Follow-Up Only			
• Consent Withdrawal: All Follow-Up			
Off Treatment		X	
Lost to Follow-up ²	X	X	X
ACCRU Deviation Form ²	X	X	X

1. Prior to 3rd and subsequent odd cycles (until PD). Upload a copy of documentation of progression in RAVE on the Supporting Documentation Form.
2. Submit only if applicable.
3. Day 1 of each cycle, beginning with Cycle 1 (until PD).
4. Day 15 of each cycle, beginning with Cycle 1 (until PD).

Follow-up Material(s)

CRF	Event Monitoring Phase ¹				
	q. 6 months until PD ²	At PD ²	After PD q. 6 mos.	Death	At Each Event Occurrence
Patient Status: Survival and Disease Status Follow-Up/Event Monitoring	X ²	X ²	X	X	
Adverse Events: Late ³					X
Notice of New Primary ³					X
Consent Withdrawal (choose appropriate form) ³					X
• Consent Withdrawal: Specimen Only					
• Consent Withdrawal: Clinical Follow-Up Only					
• Consent Withdrawal: All Follow-Up					
Lost to Follow-Up ³					X
ACCRU Deviation Form ³	X ³	X ³	X ³	X ³	

1. If a patient is still alive 3 years after registration, no further follow-up is required.
2. Upload a copy of documentation of progression in RAVE on the Supporting Documentation Form.
3. Submit only if applicable.

19.0 Budget

19.1 Each site should review the test schedule (Section 4.0), taking into account local and regional coverage policies, to determine which items are standard of care and which are research at their site. Refer to the payment synopsis for funding provided per accrual for covering study costs, as well as any additional invoiceables that may be allowed.

19.2 Tests to be research funded:

19.21 Mandatory archival tissue collection

19.22 cfDNA

19.3 Other budget concerns:

19.31 Clovis will provide rucaparib free of charge to patients while they are participating in this study.

19.32 Ipsen will provide irinotecan liposome free of charge to patients while they are participating in this study.

